7.4.6.4 Final visit

- Concomitant Drug Evaluation: See 7.4.6.2
- Urine Pregnancy Test: See 7.4.6.2
- Vital Signs: See 7.4.6.2
- BCVA: See 7.4.5.8
- Tear Film Rupture Time: See 7.4.5.2
- Ocular Surface Staining: See 7.4.5.3 and 7.4.5.4
- Comprehensive ophthalmologic evaluation: See 7.4.6.2
- IOP: See 7.4.5.9
- AE Evaluation: Ver 7.4.5.7
- OSDI: See 7.4.6.2

- Evaluation of the subject's diary: Refers to the review of the subject's diary instrument by the PI or the staff of the designated center; it will be reviewed that it is correctly filled in, as well as the patient's comments, of these comments the PI may interrogate for AEs. At the discretion of the PI, comments may or may not be reported as AEs.
- Evaluation of adherence: See 7.4.6.4
- Return of IP and subject's diary: refers to the subject's return of the IP and the subject's diary to the research center.

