7.4.5.7 Adverse events

As defined in section 8.1.1, an AE is any unfavorable medical occurrence in a subject to whom an IP is administered, regardless of causal attribution.

Management of AEs will be performed as described in the Adverse Events section.

The PI will record in the corresponding section of the eCRF the AEs that the study subjects present, in addition to referring them to the clinical file.

For an adequate evaluation of AEs, in addition to directed questioning, it is necessary to perform the Comprehensive Ophthalmological Evaluation at each visit, which consists of: ophthalmological examination of the eyelids and adnexa; anterior and posterior segment that is performed in a routine ophthalmological check-up, whose procedures are not specifically included in the study variables. Posterior pole evaluation can be with direct or indirect ophthalmoscopy, with or without pharmacological mydriasis, at the discretion of the PI. An assessment of the fundus will be carried out in search of abnormalities that alter the result of the study. IOP will be measured in this evaluation, with the instrument chosen by the PI, it should be measured after the evaluation of stains. The result of the assessment will be recorded in the clinical file. In the eCRF, only the findings that are considered so by the PI will be reported as AEs.

The AEs expected for the use of PIs are: blurred vision, burning, eye irritation, foreign body sensation, and sticky eyelash sensation. They are expected to be transient, lasting no more than 30 seconds after IP instillation, and to be of mild intensity.

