7.4.6.3 Follow-up visit

- Concomitant Drug Evaluation: See 7.4.6.2
- Vital Signs: See 7.4.6.2
- BCVA: See 7.4.5.8
- Tear Film Rupture Time: See 7.4.5.2
- Ocular Surface Staining: See 7.4.5.3 and 7.4.5.4
- Comprehensive ophthalmologic evaluation: See 7.4.6.2
- IOP: 7.4.5.9
- AE Evaluation: Ver 7.4.5.7
- Adherence assessment: Adherence will be assessed in two ways, one through the initial vs. final weight of the medication bottle and the other through the record of applications in the subject's diary, adherence will be calculated. Adherence will be calculated based on the dosage of 2, 4 and 6 applications per day.

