8.1.1 Meaning of adverse event

According to the ICH, an AE is any unfavorable medical appearance in a patient under clinical investigation who is administered a pharmaceutical product, regardless of causal attribution.

Therefore, an AE can be any of the following: any unfavorable and unintentional disease, symptom, or sign (including an abnormal laboratory finding) that is temporally related to the use of a medical product, whether or not it is considered related to such a product; any new illness or exacerbation of an existing disease (worsening of the nature, frequency, or severity of a known condition); relapse of an intermittent medical condition (e.g., headache) not present at baseline; any deterioration in a laboratory value or other clinical test (e.g., electrocardiogram [ECG], x-ray) that is related to symptoms or that results in a change in study treatment or concomitant treatment or discontinuation of study medication.

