8.1.3 Responsibilities of the researcher

It is the responsibility of the Investigator to verify AEs through questioning, review of the information recorded in the subject's diary, pertinent physical examination, assessment of evolution, as well as appropriate medical and pharmacological management; as well as to follow up until the resolution or outcome and definitive discharge of the AE, following the definitions determined in national and international regulations. [54] [55] [56]

In the event of AE or any event that puts the health and well-being of the subjects at risk, pertinent medical care will be provided, either at the research center or will be referred to the Hospital Center with the highest resolution power with which the research center has a medical care agreement. The PI will notify the sponsor's clinical monitor, according to the times established in national and international regulations. In the case of serious AEs, notify the sponsor and record the corresponding information in the eCRF and in turn, inform the REC and the Research Committee (RC).

The attention of the AEs will be carried out according to the event attention diagram (see Figure 5. Adverse Event Care).

In the final report to be written by the Clinical Team of the Medical Management of Laboratorios Sophia, S.A. de C.V., the report of AEs in compliance with current national and international regulations will be included. [55] [54]

If the research subject debuts during their participation in the study with any chronic AE, such as diabetes or systemic arterial hypertension, they will be referred to the competent health professional for chronic treatment. The follow-up and termination of your participation will be in accordance with the stipulations of the ICH.

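### Diary comments become AEs at the unblinded investigator's discretion, with no criterion tied to the AE definition, and the visit lists name their review for AEs only at the final visit

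*Combined protocol and SAP*

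**What the plan says.** Section 7.4.6.4 (final visit) has the PI or site staff review the diary for correct completion and for the subject's comments. On follow-up it says "of these comments the PI may interrogate for AEs", and on reporting "At the discretion of the PI, comments may or may not be reported as AEs". Both steps are optional, and no rule guides either one.

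The definition is broad. Section 7.4.5.7 states that "an AE is any unfavorable medical occurrence in a subject to whom an IP is administered, regardless of causal attribution", and section 8.1.1 includes "any unfavorable and unintentional disease, symptom, or sign". Section 8.1.3 lists, among the investigator's means of verifying AEs, "review of the information recorded in the subject's diary", without naming a visit.

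For the day-15 visit, section 7.4.6.3 lists "AE Evaluation: Ver 7.4.5.7" and gives the diary one use, adherence: "the other through the record of applications in the subject's diary". It does not mention comments.

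Section 7.4.2 makes AE incidence the primary safety outcome, evaluated at days 15 and 31. Section 4.2 says the study is not blinded.

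**The concern.** Under sections 7.4.5.7 and 8.1.1, judgement belongs to cause, severity and expectedness. Whether a qualifying complaint is recorded at all should not be optional. Section 7.4.6.4 contains no such limit: a PI who reads a comment about burning after the drops may leave it out and still comply with the protocol.

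Three features make this relevant to the comparison.

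- The PI knows whether the subject is on 2, 4 or 6 applications a day. Section 10.1.1 blinds the statistical personnel to avoid interpretation bias, but selection at the site happens before the data reach them.
- The expected AEs in section 7.4.5.7 (blurred vision, burning, irritation, foreign body sensation, sticky lashes) are mild and should last no more than 30 seconds after instillation. Examination days later is unlikely to show them, and a subject may forget them when questioned. The diary is the record made closest to the event.
- The safety objective in section 3.2 concerns unexpected, product-related AEs. If a comment is dropped because the PI regards it as expected, it never enters the AE record and that classification cannot be checked.

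**Working it through.** The plan states no figure on this point, so the check sets the provisions side by side.

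| Question | Provision | Reading |
|---|---|---|
| What is an AE? | 7.4.5.7, 8.1.1 | Any unfavorable occurrence, symptom or sign, whatever the cause. 8.1.1 also refers to new illness, to exacerbation of existing disease, and to relapse of a condition not present at baseline |
| Is the diary a source for AEs? | 8.1.3 | Yes, as a general duty, with no visit named |
| Must the PI ask about comments? | 7.4.6.4 | No, optional |
| Must a qualifying comment be reported? | 7.4.6.4 | No, discretionary and without a criterion |
| Are comments read at day 15? | 7.4.6.3 | AE evaluation is listed; the diary is listed for adherence only |
| Are comments read at day 31? | 7.4.6.4 | Yes |
| When is AE incidence evaluated? | 7.4.2 | Days 15 and 31 |

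The schedule (section 1.3) has one mark for return and evaluation of the diary. Its column cannot be read in the extracted table, so it carries no weight here.

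**Timing.** If a site follows the visit lists literally, a comment written between day 1 and day 15 is first read for AEs at day 31. That is 31 − 15 = 16 to 31 − 1 = 30 days later, after the 30-day treatment has ended. A site that follows section 8.1.3 may read it at day 15. The documents support both practices.

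**Exposure.** Applications per eye over 30 days are 30 × 2 = 60, 30 × 4 = 120 and 30 × 6 = 180, a ratio of 180/60 = 3. This is a ratio of opportunities for an instillation symptom. AE results are expressed in number of subjects (section 10.1.2), so incidence need not rise threefold.

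**Sensitivity only.** The documents give no AE rates, so every rate and capture fraction here is an assumption. Capture means the fraction of events recorded by any route. For two arms of n = 47, two-sided 0.05, normal approximation and no multiplicity adjustment, with p̄ the mean of p₁ and p₂:

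power = Φ{ ( |p₁ − p₂| − 1.96·√[2p̄(1 − p̄)/n] ) / √[(p₁(1 − p₁) + p₂(1 − p₂))/n] }

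- True rates 10% and 30%, full capture: (0.20 − 1.96 × 0.0825)/0.0799 ≈ 0.48, power about 68%.
- The same rates with equal capture in both arms: about 56% at 80% capture, 43% at 60% (recorded rates 6% and 18%), 30% at 40%.
- Equal true rates of 30% with unequal capture: the chance of declaring a difference is about 10% at 90% against 70% (recorded 27% and 21%), and about 30% at 90% against 50% (27% and 15%).

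These figures show direction: incomplete capture weakens a real contrast, and unequal capture can create a false one. They do not estimate what will happen in this trial.

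**The case against.** The strongest reply is that the sentence concerns comments, and someone must decide whether a free-text remark is an AE at all. That is right. A reader might infer that symptoms in the diary become AEs only if the PI wishes, in direct contradiction of section 8.1.1. The documents do not go that far, since sorting comments can be a way of applying the definition. What remains is that nothing requires the PI to sort them by that definition.

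A reader might also infer that early symptoms necessarily go unnoticed until day 31. This is not established either. Section 7.4.5.7 calls for directed questioning and examination at each visit, section 7.4.6.5 allows unscheduled visits to report AEs, and section 8.1.3 sets a general duty of diary review. The fault is inconsistency between passages.

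Nor is the whole primary safety outcome filtered. OSDI, TFRT, staining, hyperemia, chemosis, BCVA and IOP become AEs by fixed rules (sections 7.4.5.1 to 7.4.5.6, 7.4.5.8 and 7.4.5.9), and section 7.4.5.7 already calls the instillation symptoms expected AEs. The route at risk is narrow: subjective complaints that appear only in a comment.

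Finally, recording every symptom entry as an AE would go too far. Subjects enter with symptomatic dry eye (OSDI 13 to 32), and grittiness, pain and blurred vision are OSDI items. Unchanged baseline disease would then be counted as safety events. That objection stands in full, so the rule needs a baseline qualifier.

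**Conclusion.** The point holds in a limited form. Section 7.4.6.4 allows an unblinded PI to leave out a diary comment that meets section 8.1.1, and sections 7.4.6.3, 7.4.6.4 and 8.1.3 do not agree on when comments are read for AEs, although day 15 is an evaluation time for the outcome. Section 7.4.5.7 has a parallel weakness: examination findings enter the eCRF as AEs only if the PI considers them to be AEs, again without a criterion.

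The effect is confined mainly to mild, transient, subjective complaints missed by questioning and outside the threshold rules. Its size cannot be derived from the documents. A reader might take the sensitivity figures, or the threefold range in applications, as evidence that a dosage gradient in AEs will be hidden or created. Neither supports that conclusion: the first rests on assumed rates and the second counts drops, not subjects. This is a clarification worth making because it is cheap and protects the primary safety outcome. It does not show that the safety comparison is invalid.

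**What to change.** 1. In section 7.4.6.4, replace the discretion sentence with: *every diary comment describing an unfavorable symptom or sign that is new or worse than at baseline (section 8.1.1), including expected instillation symptoms, is recorded in the eCRF as an AE; the PI's judgement covers diagnosis, severity, seriousness, causality and expectedness.*
2. In the same section, make questioning on diary comments mandatory: the PI *will question* the subject about them.
3. Add review of diary comments for AEs to the day-15 list (section 7.4.6.3) and to the schedule (section 1.3), so that both agree with section 8.1.3.
4. Align the sentence on examination findings in section 7.4.5.7 with the definition in section 8.1.1.

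The cost is protocol wording, a few minutes at day 15 with a diary already used there for adherence, and somewhat more mild AEs recorded. The baseline qualifier keeps unchanged dry-eye symptoms out of the safety count.

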7.4.6.5 Unscheduled follow-up visits

At the request of the patient or any other individual involved in the study, unscheduled follow-up visits may be conducted for the reporting of AEs. During these visits, all pertinent data on the AEs reported should be collected and, where appropriate, an appropriate management plan should be established.

7.4.7 Data collection

7.4.7.1 Source documents

Source documents are all written or printed records derived from automated processes (e.g., printouts of laboratory results issued by automated analysis equipment) where the information is recorded for the first time and that is part of the permanent records of the patient's history. Examples of source documents are the medical history, clinical evolution notes, laboratory reports, cabinet study reports, nursing notes, follow-up notes, surgery records, etc.

The PI is obliged to accept the monitoring of the information related to the study, audits, review by ethics and research committees, and inspections by the health authority, this obligation implies direct access to the source documents.

7.4.7.2 Electronic forms of data collection

All data related to the protocol will be captured through an eCRF by the investigation team staff. The data related to the protocol should NOT be captured directly in the eCRF, but should be transcribed from the corresponding source document. This procedure allows monitoring to be carried out for

verify the information captured in the eCRFs. It is the responsibility of the researcher to ensure that the information is transcribed into the eCRFs in a correct, complete, and timely manner. It is understood that all eCRF forms captured and submitted for data analysis are approved by the Investigator.

7.4.7.3 File

The data collected in this database is anonymous (it only stores the patient number data along with other information of interest). The program used for data capture and storage covers the traceability requirements necessary for the execution of clinical studies. The data collected will be stored by the sponsor or the clinical research organization designated for this purpose and its storage will have a duration of 10 years. The patient number assignment records will remain in the participating institutions in charge of the PI or his work team and must be kept for at least 5 years.

8. Evaluation and management of adverse events

8.1 Regulation and standards on adverse events

The registration and reporting of AEs will be carried out in accordance with the guidelines established in NOM-220-SSA1-2016, which is in accordance with the international guidelines ICH E6.

8.1.1 Meaning of adverse event

According to the ICH, an AE is any unfavorable medical appearance in a patient under clinical investigation who is administered a pharmaceutical product, regardless of causal attribution.

Therefore, an AE can be any of the following: any unfavorable and unintentional disease, symptom, or sign (including an abnormal laboratory finding) that is temporally related to the use of a medical product, whether or not it is considered related to such a product; any new illness or exacerbation of an existing disease (worsening of the nature, frequency, or severity of a known condition); relapse of an intermittent medical condition (e.g., headache) not present at baseline; any deterioration in a laboratory value or other clinical test (e.g., electrocardiogram [ECG], x-ray) that is related to symptoms or that results in a change in study treatment or concomitant treatment or discontinuation of study medication.

8.1.2 Relevant definitions to the classification of adverse events

Severity (serious/non-serious), also called seriousness (serious/non-serious). Serious or serious is defined as any event that: results in death, threatens life, requires hospitalization, or prolongs hospitalization, is a cause of permanent or significant disability or disability, is the cause of alterations or malformations in the newborn, other medically important conditions.

Severity (mild, moderate, or severe). Mild are those that present with minimal symptoms, do not require treatment or suspension of the medication; moderate, when they interfere with usual activities, without threatening the patient's life, require treatment and may or may not require discontinuation of the medication; severe, those that interfere with usual activities and require pharmacological treatment and discontinuation of the medication.

Causality. It is the relationship that is assigned between the drug and the AE: certainly caused by the drug, there is clear evidence of causality, i.e. the AE reappears with the administration of the drug; probably caused by the drug, there is a high suspicion of causality but there is no direct evidence or it is considered unnecessary or dangerous, i.e. the reaction disappears when the drug is stopped; possibly caused by the drug, there is additional information to suggest that the cause may be due to

another drug or disease; unlikely to be caused by the drug, there is a clear explanation of the origin due to the underlying disease or the use of another drug; conditional, there is a lack of data to issue a clear causality; non-classifiable, those for which once all possible information has been obtained about the AEs, it remains unclassifiable.

8.1.3 Responsibilities of the researcher

It is the responsibility of the Investigator to verify AEs through questioning, review of the information recorded in the subject's diary, pertinent physical examination, assessment of evolution, as well as appropriate medical and pharmacological management; as well as to follow up until the resolution or outcome and definitive discharge of the AE, following the definitions determined in national and international regulations. [54] [55] [56]

In the event of AE or any event that puts the health and well-being of the subjects at risk, pertinent medical care will be provided, either at the research center or will be referred to the Hospital Center with the highest resolution power with which the research center has a medical care agreement. The PI will notify the sponsor's clinical monitor, according to the times established in national and international regulations. In the case of serious AEs, notify the sponsor and record the corresponding information in the eCRF and in turn, inform the REC and the Research Committee (RC).

The attention of the AEs will be carried out according to the event attention diagram (see Figure 5. Adverse Event Care).

In the final report to be written by the Clinical Team of the Medical Management of Laboratorios Sophia, S.A. de C.V., the report of AEs in compliance with current national and international regulations will be included. [55] [54]

If the research subject debuts during their participation in the study with any chronic AE, such as diabetes or systemic arterial hypertension, they will be referred to the competent health professional for chronic treatment. The follow-up and termination of your participation will be in accordance with the stipulations of the ICH.

8.1.4 Adverse event registration in the electronic case report form

AE registration considers:

- Subject identification information such as: subject number, age, gender, and if applicable

specify the eye.

- Information about the causality of the AE, its relationship to PIs, or to another study-related drug, as appropriate.
- Important date information:
 - Date on which the AE occurs.
 - Date on which the PI becomes aware of it.
 - Date of resolution or outcome, as applicable.
- Information on diagnosis and clinical management.
- If a lack of therapeutic response to PIs is detected, it must be reported as a serious AE within the period stipulated by current regulations. Include in concomitant medications the therapy used for the pharmacological management of the AE.
- Record the outcome or resolution of the event:
 - Recovered/resolved without sequelae
 - Recovered/resolved with sequelae
 - Not Recovered/Unresolved
 - Patient who died due to AEs
 - Patient who died and it is judged that the drug may have contributed
 - Patient who presented death and it is not related to the product or drug under investigation,
 - Unknown
- Information about the investigational product or drug or the drug associated with the AE, AMR, or SRAM. As applicable, the information concerning the generic name, distinctive name or code of the IP and/or investigational drug must be recorded, as appropriate according to the methodological design of the study, this is relevant in the case of blinded studies or in those where placebo is used as comparators, since there are circumstances that justify the opening of the blind to determine if the AE may be attributable to the active agent. the combination of active agents, or the pharmacologically inert substance(s), such as vehicles or additives, as appropriate to the phase of clinical research in which the development of the drug is located. It will also be necessary to include the data concerning the batch number, manufacturing laboratory, expiration date, dose, route of administration, start and end dates of administration and/or consumption, reason for prescription; according to whether it is an investigational product or drug (protocol in which the patient currently participates) or is a drug that the research subject consumes for the treatment of underlying concomitant

diseases or uses for the management of some transitory sign or symptom that does not correspond to the Natural History of the pathology that motivated his or her entry into the research protocol.

- Indicate the withdrawal or maintenance of the medication, as appropriate. Indicate whether the withdrawal of the IP or investigational drug or suspected drug (of causing the event) eliminates the AE. Also indicate if a dose adjustment is made, if the event changes in terms of intensity or seriousness, persistence of the reaction. It is important to indicate whether in those subjects who are exposed again to the drug, which had previously been discontinued, the AE reappears.
- Information regarding concomitant pharmacotherapy. Indicate the generic name, dose, route of administration, start and end dates of use, as well as the reason for the prescription regardless of whether it is in accordance with the information to prescribe or technical data sheet or is used outside the regulations or what has been authorized by the local, national or international regulatory entity.
- Relevant medical history information. The analysis of the AE considers the information previously narrated, despite the clinical context in which this harmful phenomenon occurs in the participants of the clinical research protocol, is of special interest, so the information about previous conditions, hypersensitivity or allergy phenomena, previous surgical procedures, laboratory analyses or cabinet examinations that have been performed on the participant, etc., that the researcher deems it appropriate to mention may do so.

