7.4.5.1 OSDI Score

The OSDI is a validated and reliable instrument to measure the severity of dry eye, it has the necessary psychometric properties to be used as an outcome variable in clinical studies. [49] It consists of a questionnaire with 3 questions and 12 items, the answer is in frequency and offers 5 options from 4 (at all times) to 0 (at no time), questions 2 and 3 also contain the NA option. (See: 16.1) The OSDI score is calculated based on the following formula:

$$\text{OSDI} = \frac{D \times 25}{E}$$

Where:

D = sum of the points of the questions answered

E = number of items answered, those answered with NA are not counted as answered

The OSDI score will be recorded on the electronic Case Report Form (eCRF).

Management as AE: An increase of more than 40% in the value of the OSDI score at the basal visit should be reported and managed as an AE for lack of effectiveness.

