7.4.5.2 Tear film rupture time

One of the first aspects of the tear film to change when there is an alteration to the ocular surface is its stability. In general, if the corneal or conjunctival surface is damaged, it is unlikely that a stable tear film can be maintained.

The most common method of assessing tear film stability is fluorescein evaluation of TFRT. Once the fluorescein has been instilled, the cobalt blue filter asks the patient not to blink after blinking 1 to 2 times. The fluorescein-colored precorneal layer will change to less fluorescent or non-fluorescent regions. The time that elapses from the last blink to the appearance of these regions is the TFRT. It will be reported in seconds, in the clinical record and in the eCRF.

Management as AE: a decrease in TFRT of more than 40% compared to baseline should be reported and managed as an AE due to lack of efficacy.

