11.3 Early termination of the study

The study may be temporarily suspended or terminated prematurely if there is a sufficiently reasonable cause. Written notice, documenting the reason for the suspension or early termination, shall be delivered by the party enforcing the suspension. The PI must promptly inform the study participants, RC, and the IRC providing the reasons.

Situations in which the suspension or early termination of the study will be contemplated include, but are not limited to:

1. The presence of serious AEs in more than 10% of participants in a study group.
2. The regulatory authority (COFEPRIS) considered it for safety alerts.
3. The Sponsor determined it for its convenience or eventualities such as: financial

support, manufacturing errors, etc.

4. The identification of unexpected risks to the participants, which are significant or unacceptable.
5. Obtaining new relevant safety information.
6. Insufficient adherence to the requirements of the protocol.
7. The data obtained are not assessable or are not sufficiently complete.
8. The determination that the primary objective has been achieved.
9. The determination of futility.

In the event of suspension, the study may be resumed once the situations that led to the suspension have been corrected; as long as this justification is sufficient for the sponsor, RC, REC and regulatory authorities.

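### Section 8.1.4 makes any detected lack of response a serious AE with no threshold, against 7.4.5.1, 7.4.5.2 and 8.1.2, so efficacy failures enter the serious-AE count and the 10% ground in 11.3

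*Combined protocol and SAP*

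**What the plan says.** Five places in the combined protocol and SAP bear on how a treatment failure is classified.

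- Section 8.1.4, on recording AEs in the eCRF: "If a lack of therapeutic response to PIs is detected, it must be reported as a serious AE within the period stipulated by current regulations". It neither defines lack of response nor sets a cut-off.
- Section 7.4.5.1: an OSDI increase of more than 40% over the basal visit "should be reported and managed as an AE for lack of effectiveness".
- Section 7.4.5.2: "a decrease in TFRT of more than 40% compared to baseline should be reported and managed as an AE due to lack of efficacy".
- Section 8.1.2 defines seriousness by outcome: "Serious or serious is defined as any event that: results in death, threatens life, requires hospitalization", and so on through disability and malformation to an open item for other medically important conditions. Lack of response is not named.
- Section 11.3 lists, as its first ground, "The presence of serious AEs in more than 10% of participants in a study group", with no category of serious AE left out. Its ninth ground is "The determination of futility". The list opens with "Situations in which the suspension or early termination of the study will be contemplated include, but are not limited to".

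Section 8.1 adds that "The registration and reporting of AEs will be carried out in accordance with the guidelines established in NOM-220-SSA1-2016", a national standard whose text is not part of the documents.

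**The concern.** The sections give a site different instructions for the same subject. If OSDI has risen by 45%, 7.4.5.1 says AE and 8.1.4 says serious AE. If OSDI is unchanged, 7.4.5.1 calls for nothing, while 8.1.4 could be read to require a serious-AE report, since it does not say how poor a response must be.

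The label has consequences inside the protocol. A serious AE must reach the clinical monitor within 24 hours (8.1.6) and be reported to the ethics and research committees (8.1.3). It also counts towards the first ground of 11.3. That ground reads as a safety ground, and 11.3 already has a separate entry for futility. The serious-AE totals in the final report would mix harm with lack of benefit, and could differ between centres according to how each reads 8.1.4.

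AE incidence, the primary safety outcome, does not change with the seriousness label. It does depend on which threshold makes a poor response an AE at all.

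**Working it through.** **1. The texts side by side**

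| Section | Trigger | Class |
|---|---|---|
| 7.4.5.1 | OSDI up more than 40% | AE |
| 7.4.5.2 | TFRT down more than 40% | AE |
| 8.1.4 | lack of response detected, no cut-off | serious AE |
| 8.1.2 | listed outcomes plus an open item | serious; lack of response not named |
| 11.3, first ground | any serious AE, more than 10% of a group | suspension or termination considered |

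Reading 8.1.4 as meaning only the 40% events removes the threshold conflict but not the class conflict: those events would still be serious in 8.1.4 and plain AEs in 7.4.5.

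**2. When the 10% ground is met**

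The planned group is 47 (10.2.2): 39 × 1.2 = 46.8, rounded up, and 3 × 47 = 141, as the plan states. The smallest whole number above 0.10 × 47 = 4.7 is 5. Check: 5/47 = 10.6% and 4/47 = 8.5%. With only the 39 subjects before the loss allowance, it would be 4 (4/39 = 10.3%).

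**3. Chance of reaching 5 of 47, for scale only**

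Inputs: mean OSDI change of −20% (the assumption in 10.2.2). The SD of percent change is not in the documents, so SDs of 20 to 60 percentage points are assumed. Two models are used: a normal percent change, and a lognormal final-to-baseline ratio with mean 0.8 and the same SDs. The second is included because the normal model permits falls beyond −100% (9% of subjects at SD 60).

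Formulas: p = P(change > 40%), then P(X ≥ 5) with X ~ Binomial(47, p). Example, normal, SD 40: p = 1 − Φ((40 + 20)/40) = 1 − Φ(1.5) = 0.0668, giving P(X ≥ 5) = 0.20.

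Under the documents' own 40% threshold:

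| SD | p, normal | P(X ≥ 5) | p, lognormal | P(X ≥ 5) |
|---|---|---|---|---|
| 20 | 0.0013 | 0.00 | 0.0083 | 0.00 |
| 30 | 0.0228 | 0.00 | 0.0423 | 0.05 |
| 40 | 0.0668 | 0.20 | 0.0777 | 0.30 |
| 50 | 0.1151 | 0.64 | 0.1035 | 0.54 |
| 60 | 0.1587 | 0.89 | 0.1207 | 0.68 |

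If a site instead took lack of response to mean no improvement (change of 0 or more), p would be 0.16 to 0.37 (normal) or 0.15 to 0.25 (lognormal), and P(X ≥ 5) would be 0.86 to above 0.99. The documents do not state that reading; it shows only what the missing threshold leaves open.

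**4. What these figures do not measure**

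They describe one arm in which all 47 subjects have a final OSDI. OSDI is scored only at the basal and final visits (Study Schedule, 1.3), so an OSDI-based event arises at the end of that subject's treatment. The chance of crossing 10% while recruitment or treatment continues is smaller and was not computed. TFRT-based events, which can appear at day 15, are not included.

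**The case against.** The strongest reply is that the sections can be reconciled. Sections 7.4.5.1 and 7.4.5.2 say when lack of efficacy is an event, and 8.1.4 says how it is registered. A serious AE is also an AE, and neither 7.4.5 section says non-serious. The 40% rule is the only lack-of-efficacy threshold in the documents, so it is the natural meaning of a detected failure. Section 8.1.4 also looks like generic text, since it discusses blinding and placebo, which this trial does not use. This is a fair account of what was probably meant, but 8.1.4 does not say it, and the difference in class remains.

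Second, the national standard cited in 8.1 may itself require the serious class. That cannot be checked from the documents. If it does, the reporting duty in 8.1.4 is right, and the plan should state it as a regulatory duty distinct from the 8.1.2 definition.

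Third, 11.3 is discretionary. Suspension needs a reasonable cause, the list is open, and futility leads to the same choice. This stands. A reader might infer that ordinary non-responders would halt the trial. The documents do not support that: there is no automatic stop, the high probabilities rest on a no-improvement reading that is never stated, and OSDI results come only at a subject's final visit.

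Fourth, a reader might infer that lack-of-efficacy events should simply be removed from the 10% count. That goes too far. OSDI items include eye pain, grittiness and blurred vision (Annex 16.1), and the expected AEs in 7.4.5.7 include blurred vision, irritation and foreign body sensation. A large OSDI rise could be product irritation, possibly related to dosing frequency, and outright exclusion could hide it. This objection stands and shapes the fix.

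**Conclusion.** The inconsistency is in the text and needs no assumption: 8.1.4 assigns the serious class without a threshold, 7.4.5.1 and 7.4.5.2 assign the AE class at more than 40% worsening, and 8.1.2 does not name lack of response. As written, efficacy failures enter the serious-AE count and the discretionary first ground of 11.3, which 5 of 47 subjects would meet.

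The likelihood is unknown. Under the 40% threshold, the completed-arm probability runs from about 0 to 0.89 (normal) or 0.68 (lognormal) over the assumed SDs, and is at most 0.05 at SDs of 20 to 30. That range cannot support a claim that the ground is likely to be met. Nor do the documents show that reporting these events as serious is itself wrong, because the governing standard is not included.

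The point should be corrected, with medium confidence. It concerns safety classification and reporting and leaves the primary efficacy analysis untouched.

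**What to change.** - **Section 8.1.4:** define lack of therapeutic response by the more-than-40% OSDI and TFRT thresholds of 7.4.5.1 and 7.4.5.2. Class it as serious only if it meets 8.1.2. State separately any reporting class or timeline that regulation requires.
- **Final report:** list lack-of-efficacy events apart from other AEs and serious AEs.
- **Section 11.3, first ground:** do not exclude these events. Show the 10% count with and without events that are serious solely because of the 8.1.4 lack-of-response rule. Always keep in the count any event that meets 8.1.2 on its own.

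The separate listing and the double count remain useful even if regulation fixes the serious class. The cost is wording in two sections, one extra listing and one extra count. Sample size, visits and the efficacy analysis do not change.
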